#### **d. Recruitment/ Selection**

- *Potential participants will be recruited through the MS or CNS inflammatory disease clinics of the six participating hospitals with a cap of 20 participants at any single centre. Participants will not be financially compensated for their involvement in this trial but will be reimbursed for any reasonable costs of participation (e.g. parking costs).*
- *Participants will be recruited by neurologists at each site, who having identified a patient who is about to commence treatment with alemtuzumab, will invite the pwMS to participate in the trial. Potential participants will be provided with an introduction and overview of the study by their treating neurologist. Those who are interested in participating will be provided with the Patient Information and Consent Form (PICF) to take away and read and a further visit with one of the study investigators will be arranged at a later date.*
- *Participants will be enrolled in the study at the baseline/screening visit provided they:*
  - 1. *Have given written informed consent*
  - 2. *Meet all the inclusion criteria*
  - 3. *Meet none of the exclusion criteria*
- *Randomisation: Participants will be randomised at enrolment to treatment with rituximab or placebo at a 2:1 ratio. Randomisation will be performed using the randomisation module of the REDCap database based on a random number sequence produced in Excel®, Microsoft (Seattle, CA, USA) stratified by site, sex and age. This randomization sheet will be generated by Assoc/[name]. There will a cap of 20 participants for any single site.*
- *Blinding and allocation concealment: This will be a double-blinded study with both patient and treating physician blinded as to whether the participant is receiving active treatment or placebo. At the screening visit, participants will be assigned a unique participant Screening Number. At the baseline/enrolment visit, after eligibility is confirmed and the full consent form has been signed, a Participant Identification Number (PIDN) will be assigned. PIDNs will be randomly assigned to intervention or placebo groups according to the randomisation code provided by the randomisation sheet. Randomisation*

---

codes will only be visible through REDCap to site pharmacists who will make up the active treatment and placebo. Both rituximab and 0.9% sodium chloride (placebo) are colourless fluids, so will be indistinguishable to treating physician, participants and other staff.

- *Breaking of study blinding: The randomisation code for an individual participant may only be unblinded in emergency situations, where the Site Investigator decides a participant cannot be adequately treated without knowing the identity of their treatment allocation. The Site Investigator may contact the site pharmacy to obtain the treatment identity. If possible, such emergencies should be discussed with the Principal Investigator before breaking the blind. The randomisation code will be stored electronically by the Griffith University randomisation service. If the blind is broken for a participant, the time, date, participant number and reason for opening must be documented.*
- *On completion of the study: Unblinded study data will only be available once all data collected have been entered into the REDCap study database for every participant and the database has been finalized (locked), except in the case of an emergency, as detailed above.*

#### **e. Consent**

- *The PICF provides outline details of the clinical trial and details the expectations for both the participant and those conducting the trial. In particular, the PICF makes it clear that participation is voluntary and that participants can withdraw at any time. It is also indicated that any decision to participate or not, will in no way affect a pwMS's subsequent treatment at that facility.*
- *At the subsequent visit prior to any study-related activity, the site investigator will review the details of the study, assess the pwMS understanding of the information in the PICF and having asked the potential participant if they have any questions, answer those questions. Having established that the potential participant is fully informed and wishes to proceed in the study, the participant will provide written informed consent using the PICF. Study staff will ensure that an adequate explanation is provided to the participant and their family about the aims, the requirements of the study that need to be adhered to strictly, and any potential known and unknown risks and benefits of the study. Study staff will ensure that all questions about the study are answered adequately and that the participant understands the information provided about the study. The study staff conducting the informed consent discussion will ensure that consent is voluntary and free from coercion. The staff member that conducts the consent discussion will also sign the informed consent form. A copy of the PICF will be provided to the participant to keep.*

- 
- *Consent will be specific for this study only.*

## **f. Risk Mitigation Procedures**

- *Treatment with alemtuzumab is associated with a risk (6-8%) of reactivation of HSV2 infection during the first month and a much lower level risk of listeria meningitis over the same time period. As is our usual practice all participants will receive valaciclovir 500 mg once daily for 30 days and Bactrim DS 960mg three times per week for 4 weeks commencing on the first day of therapy.*
- *In view of the potential additive risk of rituximab and alemtuzumab causing an increased risk of infection all participants will be advised to report any symptoms of fever, headache, neck stiffness, photophobia, shortness of breath, cough, abdominal pain or skin lesions to site investigators immediately.*
- *In view of the known risk of autoimmune adverse events with alemtuzumab (e.g. 30% risk of autoimmune thyroid disease) all participants will be monitored with monthly blood and urine tests through the Bloodwatch program. This is PBS mandated online monitoring program for all pwMS undergoing therapy with alemtuzumab which is sponsored by the manufacturer. This is standard of care for this therapy and includes monthly urine tests for red cells and protein, monthly blood tests for full blood count, urea and electrolytes and 3-monthly blood tests for TSH levels.*
- *Regular lymphocyte subset counts will be monitored and rituximab administration will be delayed if B-cell counts do not exceed 30% of pre-treatment levels.*

## **g. Participant Withdrawal Procedures**

- *Screen Failure: Participants who do not meet the requirements for enrolment will be deemed to be screen failures. As such they will not be enrolled in the study and will not be randomised to any intervention or placebo. They will be given a unique trial ID and listed in the enrolment log as a screen failure. A minimal set of information (age, sex, date, reason for screen failure) will be recorded in the eRCF in order to meet the Consolidated Standards of Reporting Trials (CONSORT) publishing requirements, respond to queries from regulatory authorities and to ensure transparent reporting of screen failure participants.*
- *Lost to follow up: Investigational staff will go to all necessary lengths possible to minimise loss to follow-up (LTFU) of participants by active and continued follow-up of participants who fail to attend study visits or who are otherwise not contactable. A participant will not be considered LTFU until all routes of contact have been exhausted. If a previously lost participant is*

---

retrieved within 2 weeks of the relevant study visit, they will be brought into the relevant study visit as soon as possible for the relevant measures such as primary endpoint determination. If a participant wishes to drop out due to study burden, the trial coordinator and site nurse will negotiate with the participant to reduce trial duties with a focus on continued collection of data relating to the primary outcome. If the participant wishes to drop out for health reasons (such as intolerable adverse events), the final assessment visit will be brought forward.

- *Stopping Rules: Participants will be able to withdraw from the study at any time by their own volition with no impact on any future care they may require from the recruitment site. Participants may also by their own volition choose to cease the study treatment at any time but remain in the trial with continued follow-up until the end of the study; this will have no impact on any future care they may require in the participating clinics. If the participant experiences a serious adverse event (SAE) that is suspected to be linked to the study medication or compromises the participant's ability to adhere to the intervention, the intervention will be ceased; however, the participant will remain in the trial and will be followed-up through to the end of the study.*

## **h. Study Procedure**

- *Treatment Arms*
- *Arm 1: Intervention*
- *Arm 2: Placebo*
- *Intervention Description, Dosage and Route of Administration*
- *The investigational product is rituximab, which is a monoclonal antibody against CD20 that cause lysis of B-lymphocytes. The antibody is a humanised mouse antibody and is administered intravenously via an infusion over a period of time that varies according to the dosage (see below). The dosage to be used is 100 mg/m^2 of estimated body surface area (BSA). BSA will be estimated based on height (H) and weight (W) according to the Du Bois formula:*
- *BSA = 0.007184 x W0.425 x H0.725*
- *With height measured in cm and weight measured in kg.*
- *Dosage will be rounded down to the nearest 10 mg.*
- *Study drug will be provided as a solution of 100 mg in 10 ml vials.*
- *Infusions will be delivered at set times of 10 weeks and 30 weeks after administration of alemtuzumab in combination with 100 mg intravenous methylprednisolone to reduce the risk of infusion reactions.*
- *Placebo*

- *Placebo will be 0.9% sodium chloride, which as a colourless solution is indistinguishable from diluted rituximab.*
- *Pre-medication*
- *Prior to administration of the study drug/placebo all trial participants (intervention and placebo arms) will be administered loratadine 10 mg orally and 100 mg intravenous methylprednisolone made up in 100 ml 0.9% sodium chloride and infused over 30 minutes.*
- *Preparation and Administration of Study Drug/Placebo*
- *Study drug and placebo will be made up by non-blinded onsite pharmacists according to the randomisation schedule product information sheet for rituximab. Specifically, the calculated dose of study drug will be aseptically withdrawn from vials and diluted in 100 ml of 0.9% sodium chloride ensuring that the calculated concentration is between 1 mg/ml and 4 mg/ml. To ensure adequate mixing the bag of diluted study drug/placebo will be gently inverted to avoid foaming. The prepared drug products will be visually inspected for particulate matter or discolouration.*
- *Rituximab/placebo will be administered according to Tables 1 and 2 below:*

**Table 1: First Dose administration rate of Rituximab/Placebo**

Period	1-30 mins			31-60 mins			61-90 mins			91-120 mins			Total		
Infusion Rate	50 mg/hr			100 mg/hr			150 mg/hr			200 mg/hr					
BSA (m  )	Time (m)	Dose (mg)	Vol (ml)	Time (m)	Dose (mg)	Vol (ml)	Time (m)	Dose (mg)	Vol (ml)	Time (m)	Dose (mg)	Vol (ml)	Time (m)	Dose (mg)	Vol (ml)
1.5	30	25	16.7	30	50	33.3	30	75	50.0	0	0	0.0	90	150	100.0
1.6	30	25	15.6	30	50	31.3	30	75	46.9	3	10	6.3	93	160	100.0
1.7	30	25	14.7	30	50	29.4	30	75	44.1	6	20	11.8	96	170	100.0
1.8	30	25	13.9	30	50	27.8	30	75	41.7	9	30	16.7	99	180	100.0
1.9	30	25	13.2	30	50	26.3	30	75	39.5	12	40	21.1	102	190	100.0
2	30	25	12.5	30	50	25.0	30	75	37.5	15	50	25.0	105	200	100.0
2.1	30	25	11.9	30	50	23.8	30	75	35.7	18	60	28.6	108	210	100.0
2.2	30	25	11.4	30	50	22.7	30	75	34.1	21	70	31.8	111	220	100.0
2.3	30	25	10.9	30	50	21.7	30	75	32.6	24	80	34.8	114	230	100.0
2.4	30	25	10.4	30	50	20.8	30	75	31.3	27	90	37.5	117	240	100.0
2.5	30	25	10.0	30	50	20.0	30	75	30.0	30	100	40.0	120	250	100.0

**Table 2: Subsequent dose administration rate of Rituximab/Placebo**

Period	1-30 mins			31-60 mins			61-90 mins			Total		
Infusion Rate	100 mg/hr			200 mg/hr			300 mg/hr					
BSA (m  )	Time (m)	Dose (mg)	Vol (ml)	Time (m)	Dose (mg)	Vol (ml)	Time (m)	Dose (mg)	Vol (ml)	Time (m)	Dose (mg)	Vol (ml)
1.5	30	50	33.3	30	100	66.7	0	0	0.0	60	150	100.0
1.6	30	50	31.3	30	100	62.5	2	10	6.3	62	160	100.0
1.7	30	50	29.4	30	100	58.8	4	20	11.8	64	170	100.0
1.8	30	50	27.8	30	100	55.6	6	30	16.7	66	180	100.0
1.9	30	50	26.3	30	100	52.6	8	40	21.1	68	190	100.0
2	30	50	25.0	30	100	50.0	10	50	25.0	70	200	100.0
2.1	30	50	23.8	30	100	47.6	12	60	28.6	72	210	100.0
2.2	30	50	22.7	30	100	45.5	14	70	31.8	74	220	100.0
2.3	30	50	21.7	30	100	43.5	16	80	34.8	76	230	100.0
2.4	30	50	20.8	30	100	41.7	18	90	37.5	78	240	100.0
2.5	30	50	20.0	30	100	40.0	20	100	40.0	80	250	100.0

- 
- *First infusions will typically run over 90 – 120 minutes and subsequent infusions will run over 60 – 80 minutes.*
  - *Pulse and blood pressure will be monitored every 30 minutes from the commencement methylprednisolone and until 30 minutes after the completion of rituximab/placebo and for no less than a minimum of 2 hours.*
  - *Infusion rates should only be increased to the next phase provided there are no adverse events and that if there are symptoms of a mild infusion reaction the rate should be reduced to the previously tolerated level or if symptoms are more significant (shortness of breath, tachycardia, low blood pressure) the infusion should be discontinued and the PI notified immediately.*
  
  - *Study Drug Accountability*
  - *A nominated pharmacist at each participating site will maintain an inventory of receipt, use, return and collection of study drug.*
  - *Control of Supplies*
  - *The nominated site pharmacist at each site is responsible for recording the dispensing of the product to participants on an investigational product dispensing log which will be recorded in the eCRF. Accurate records will be maintained demonstrating dates and amount of product received, to whom dispensed and accounts of any product accidentally or deliberately destroyed. Clinical trial materials will not be loaned or dispensed to another investigator or trial centre or used for any purpose other than the trial without the prior approval of the trial coordinator and Site Investigator.*
  - *Return of Supplies*
  - *At the conclusion of the trial, the Principal Investigator or nominee will perform a final inventory. If any supplies cannot be accounted for, this will be documented on the product accountability form together with an explanation of the discrepancy. The originals of the product accountability and dispensing logs must be sent to the trial coordinator. The Principal Investigator will retain copies of these logs on file.*
  - *Retention of Samples*
  - *The Principal Investigator or delegate will maintain accurate records demonstrating dates and amount of product received, to whom dispensed and accounts of any product accidentally or deliberately destroyed. It will be the responsibility of the Principal Investigator or delegate to ensure that adequate samples of all trial doses are retained in accordance with the relevant regulatory guidelines. For example, for trials conducted under the CTN scheme in Australia, at least a sample from each batch of product used in the trial should be retained for one year longer than the shelf-life of the product, and to comply with ICH-GCP requirements, sufficient quantities of the product(s)*

---

*should be retained either until the analyses of the trial data are complete or as required by the applicable regulatory requirements, whichever represents the longer retention period.*

- *Study Procedures and Visits*
- *Participants will be required to undergo the following study procedures and visits.*
- *Screening Visit (-30 - -7 days)*
  - *Informed consent will be obtained*
  - *Completion of eligibility criteria checklist*
  - *Comprehensive review of medical history including; details of MS history, other past medical and surgical history, past and current medications, family history, social history and allergies*
  - *Comprehensive medical and neurological examination*
  - *EDSS*
  - *HADS*
  - *Baseline/enrolment Visit (-7 - -4 days)*
  - *Informed consent will be re-obtained*
  - *Review of neurological symptoms*
  - *Review of medications*
  - *EDSS*
  - *MSIS29*
  - *Blood tests – FBC, EUC, LFT, TFT, Lymphocyte subsets, bHCG (in women)*
  - *Urine screen – red cell count and albumin*
  - *UACR*
- *Alemtuzumab therapy visits (Year 1, Day 1 – 5; Year 2, Day 1-3) – part of normal care*
  - *Loratidine 10 PO od (continued for 10 days)*
  - *Valaciclovir 500 mg PO od*
  - *Bactrim DS (960 mg) PO 3 times per week (Mon, Weds, Fri)*
  - *0.9% Sodium Chloride IV 1L over 8 hours*
  - *Methylprednisolone 500 mg IV over 30 minutes*
  - *Alemtuzumab 12 mg IV over 4 hours*
  - *Hourly temperature, pulse and blood pressure*
  - *First month (Day 6 – 30) – part of normal care*
  - *Valaciclovir 500 mg PO od*
  - *Bactrim DS (960 mg) PO 3 times per week (Mon, Weds, Fri)*
  - *Bloodwatch pathology tests (Every month) – part of normal care*
  - *FBC/lymphocyte subsets (4 ml) – lymphocyte subsets will be performed at weeks -1, 4, 9, 13, 26, 35, 50, 57, 61, 65, 78, 83 and 104.*
  - *EUC/LFTs (10 ml)*
  - *Urine red cell count*

[figure not shown]
- *Urine albumin*
- *UACR*
- *TSH (every 3rd month)*
- *Intervention visits (At weeks 10 and 30 provided B-cell count >30% of pre-treatment level.*
  - *Loratidine 10 mg PO 30 minutes prior to rituximab.*
  - *Methylprednisolone 100 mg IV over 30 minutes, commencing 30 minutes prior to rituximab.*
  - *Rituximab 100 mg per m^2 or placebo IV over 1 hour*
- *Monitoring visits (Every 6 months – weeks 25, 51, 77, 103, 129)*
  - *Review of relapse history*
  - *Review of adverse events*
  - *Review of intercurrent illness*
  - *Review of concomitant medications*
  - *EDSS*
  - *Monitoring visits may be conducted remotely via telehealth whether for reasons of COVID-lockdowns or remoteness of the participant*
- *MRI (Every 12 months – Baseline, Weeks 51, 103, 155)*
  - *MRI Brain*
  - *Closeout visit (Week 155 or earlier at close of study)*
  - *Review of relapse history*
  - *Review of adverse events*
  - *Review of intercurrent illness*
  - *Review of concomitant medications*
  - *EDSS*
  - *MSIS-29*
- *The timeline of participant involvement and total time commitment per patient in the trial is outlined in Table 3. Participants will also undergo the following procedures as part of normal care for someone receiving alemtuzumab. Admissions to day infusion centre for 8 hours on 5 days in year 1 and 3 days in year 2 for administration of alemtuzumab. They will also undergo monthly blood and urine tests as listed about through any private pathology firm convenient to them as part of the Bloodwatch® (RxMx®, Australia) monitoring program. The additional lymphocyte subset counts will be undertaken as part of the same blood draw and will not involve any additional tubes or time.*
- *Time constraint tolerance on study related procedures will be as follows:*
- *Screening visit, Enrolment, Review visit, EDSS and Screening bloods will be +/- 1 week.*
- *MRI +/- 2 weeks.*
- *Rituximab administration +/- 3 days.*

- If for clinical reasons the timing of alemtuzumab infusions must be adjusted, the timing of rituximab administration will be adjusted accordingly but the timing of all other study related procedures will remain unaltered.

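### Every dose after the first starts at 100 mg/hr with no condition on tolerance of the earlier infusion, so a non-serious reaction at 50 mg/hr can be followed by a start at twice that rate

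*Protocol*

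**What the plan says.** Protocol section 3.h gives one instruction on rate: "Rituximab/placebo will be administered according to Tables 1 and 2 below". The headings decide which table applies. "Table 1: First Dose administration rate of Rituximab/Placebo" runs at 50, 100, 150 and 200 mg/hr in 30-minute phases. "Table 2: Subsequent dose administration rate of Rituximab/Placebo" runs at 100, 200 and 300 mg/hr. Within each table only BSA varies. The text below Table 2 adds that "subsequent infusions will run over 60 – 80 minutes".

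The same text governs what happens during an infusion. A step up needs the absence of adverse events, and "if there are symptoms of a mild infusion reaction the rate should be reduced to the previously tolerated level". For shortness of breath, tachycardia or low blood pressure, the infusion is stopped and the PI is told.

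Three other provisions bear on whether a later dose is given:
- Section 3.f: "rituximab administration will be delayed if B-cell counts do not exceed 30% of pre-treatment levels". The visit list in section 3.h repeats this: "Intervention visits (At weeks 10 and 30 provided B-cell count >30% of pre-treatment level".
- Section 3.g, Stopping Rules: the intervention is ceased after a "serious adverse event (SAE) that is suspected to be linked to the study medication", or one that compromises adherence to the intervention.
- Section 3.g also lets participants stop study treatment by choice and stay in follow-up, and provides for drop-out because of intolerable adverse events.

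The intervention-visit list gives the rituximab or placebo infusion a duration of one hour.

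**The concern.** The starting rate doubles between dose 1 and dose 2, and nothing makes that depend on how dose 1 went. The first phase of Table 2 is a starting rate, not a step up, so the no-adverse-events condition on increases does not reach it. The step-down rule comes into play only after symptoms have appeared in the new infusion. A reaction that is not serious does not trigger mandatory cessation, and a B-cell count says nothing about infusion tolerance.

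The participants concerned are those who had a non-serious reaction in the 50 mg/hr phase, or who were slowed from 100 to 50 mg/hr and never tolerated 100 mg/hr afterwards, and who continue. What is at stake is their safety at the next infusion. After an infusion stopped for more significant symptoms the PI is informed, but no rule says whether, or at what rate, to re-dose.

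The one-hour duration is a separate inconsistency. Read literally at dose 1, it requires a faster infusion than Table 1 allows.

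**Working it through.** **Inputs (protocol section 3.h).** Dose 100 mg per m² of BSA; BSA rows 1.5 to 2.5, so 150 to 250 mg; 30-minute phases at the tabulated rates, the last one cut short when the dose is complete. Table 3 places the four infusions at weeks 10, 30, 62 and 82 and allows 4 hours per infusion visit.

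**1. Reproducing the stated times.** Time in a phase = dose given in the phase / rate.

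| BSA | Dose (mg) | Table 1 (min) | Table 2 (min) | Difference (min) |
|---|---|---|---|---|
| 1.5 | 150 | 30+30+30 = 90 | 30+30 = 60 | 30 |
| 2.0 | 200 | 30+30+30+15 = 105 | 30+30+10 = 70 | 35 |
| 2.5 | 250 | 30+30+30+30 = 120 | 30+30+20 = 80 | 40 |

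All 11 BSA rows of both tables reproduce. The tables are internally correct.

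**2. Starting rate of dose 2 against the rate at which dose 1 caused a reaction.**
- Reaction at 50 mg/hr: 100/50 = 2.0 times. Table 1 has no lower rate to return to.
- Reaction at 100 mg/hr: 100/100 = 1.0 times, which is 100/50 = 2.0 times the rate to which the participant was slowed.
- Reaction at 150 mg/hr: 100/150 = 0.67 times.
- Reaction at 200 mg/hr: 100/200 = 0.5 times.

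Only the first two are a problem. In the last two, dose 2 starts below the rate that caused symptoms, and each later step up requires no adverse events.

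**3. Drug given in the first 30 minutes, before the next scheduled pulse and blood pressure check.**
- Table 2: 100 × 0.5 = 50 mg, which is 50/150 = 33% of the dose at BSA 1.5 and 50/250 = 20% at BSA 2.5.
- Table 1: 50 × 0.5 = 25 mg, which is 25/150 = 17% and 25/250 = 10%.

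**4. Exposure.** Table 2 governs up to 3 of the 4 planned infusions (weeks 30, 62 and 82). The protocol gives no reaction rate. As an assumption only: 80 × 2/3 = 53.3 rituximab participants under 2:1 allocation; at 2%, 5% or 10% with any reaction, 1.1, 2.7 or 5.3 people. The concern covers only reactions at 50 or 100 mg/hr, so these are upper bounds under each assumed rate.

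**5. The one-hour duration.** It matches no row of Table 1 (90-120 minutes) and only the BSA 1.5 row of Table 2 (60 minutes; every other row is longer, up to 80). At dose 1, one hour means an average of 150 to 250 mg/hr, against a Table 1 start of 50 mg/hr. In its first hour Table 1 delivers 25 + 50 = 75 mg, which is 75/150 = 50% to 75/250 = 30% of the dose.

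**The case against.** The best case against the point is that it describes an unstated contingency which competent staff would handle. Section 3.b says all sites have experience with rituximab, and slowing the start for a known reactor is ordinary clinical judgement. Premedication, 30-minute observations and symptom-triggered slowing all apply from the start of dose 2. That is fair, and it limits the risk. None of it changes the starting rate in the written schedule, so staff at six sites would have to depart from the protocol to do the sensible thing. The reference in section 3.h to the product information sheet does not help, because it concerns making up the drug.

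Other parts of the objection stand, and they rule out stronger readings that a reader might infer:
- *That only a B-cell count or a serious event can keep a reactor from dose 2.* Section 3.g also allows voluntary cessation and drop-out for intolerable adverse events. These are routes out of treatment, but they set no rate for those who continue.
- *That the protocol orders 60-80 minutes whatever happens.* The sentence on durations opens by describing what is typical, and that can be read to cover subsequent infusions too. Slowing or stopping for symptoms is required shortly after it.
- *That anyone slowed at 100 mg/hr is known not to tolerate it.* The protocol does not say whether the rate may be raised again once symptoms settle. If it was, and 100 mg/hr was then tolerated, a 100 mg/hr start is unobjectionable.
- *That any earlier reaction leads to a faster re-exposure.* Reactions only at 150 mg/hr or above do not.
- *That serious-looking reactions pass unnoticed.* More significant symptoms already stop the infusion and alert the PI.

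**Conclusion.** The point holds as a limited dosing-safety gap that should be corrected. Followed exactly, section 3.h starts dose 2 at 2.0 times the rate that caused a non-serious reaction at 50 mg/hr, or returns a participant to 100 mg/hr after slowing to 50 mg/hr without later tolerance of 100 mg/hr. This is the result of a stated rule, not only of missing detail.

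It rests on two assumptions: that the participant continues treatment, and that nobody departs from the tables by judgement. The number affected cannot be derived from the protocol. A reader might infer that the trial's result is threatened; the documents do not support that, since the primary analysis and power do not depend on infusion rates.

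The one-hour duration is an error on its own, whatever view is taken of the main point.

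**What to change.** In section 3.h, with identical wording for both arms so that the blind is kept:

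1. Start a subsequent infusion on Table 2 only if 100 mg/hr was tolerated at the previous infusion. Otherwise start on Table 1, and do not exceed the last tolerated rate unless the participant is free of symptoms.
2. After a discontinued infusion, or a reaction in the 50 mg/hr phase, re-dose only after PI review.
3. State that reactions only at 150 mg/hr or above do not require Table 1.
4. In the intervention-visit list, replace the one-hour duration with a reference to the rates in Tables 1 and 2.

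**Cost.** A few sentences of text. If Table 1 is completed, the infusion takes 30-40 minutes longer. With 30 minutes of methylprednisolone before and 30 minutes of observation after, the visit takes 90 + 60 = 150 to 120 + 60 = 180 minutes, within the 4 hours in Table 3.

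Holding the rate takes longer:
- Held at 100 mg/hr after the first phase: 30 + 125/100 × 60 = 105 minutes (BSA 1.5) to 30 + 225/100 × 60 = 165 minutes (BSA 2.5); visit 165-225 minutes, still within 4 hours.
- Held at 50 mg/hr throughout: 150/50 × 60 = 180 to 250/50 × 60 = 300 minutes; visit 240-360 minutes. This reaches 4 hours at BSA 1.5 and exceeds it at every higher BSA (at 1.6: 192 + 60 = 252 minutes), so sites would need to plan for a longer visit in that case.

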## c. Study Population

- *The study will aim to recruit 80 pwMS who are due to commence treatment with alemtuzumab.*
- *Inclusion criteria*
  - *Aged 18 – 55 years (inclusive)*
  - *Diagnosed with relapsing remitting MS (RRMS) by a neurologist*
  - *Diagnosis of MS meeting 2017 McDonald criteria*
  - *Diagnosed with MS within the previous 10 years*
  - *Expanded disability status scale (EDSS) score < 5.0*
  - *English speaking or non-English speaking who can ensure external interpreter assistance (e.g. relative or friend) to attend all visits for the duration of the clinical trial.*
  - *Available to attend clinic visits*
  - *Willing to sign up for and comply with Bloodwatch monitoring program*
  - *Fully vaccinated against COVID-19 (2 standard doses plus booster)*
- *Exclusion criteria*
  - *Known or suspected prior autoimmune disease (other than MS)*
  - *Any other serious co-morbidity that in the view of the investigator would preclude participation in the study*
  - *Pregnant (if female)*
  - *Currently lactating (if female)*

- 
- Unwilling or unable to use appropriate contraception for the treatment phase of the study (2 years) – male or female
  - Recent or current history of major depression, bipolar disorder, psychosis or suicidality
  - Currently or recently taking any illicit substances (including any cannabis product)
  - Allergy to valaciclovir
  - Allergy to Bactrim, Trimethoprim or Sulphur based antibiotics

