**Figure 1. RAMBLE Trial Design**

Following screening participants will be randomized 2:1 to receive either rituximab or placebo at weeks 10 and 30 after each dose of alemtuzumab. Follow up will be for a minimum of 2 years and a maximum of 4 years. Alemtuzumab administered at Week 1 and Week 53 (yellow arrows). Rituximab/placebo administered at Weeks 10 and 30 in each of Years 1 and 2 (blue arrows). Clinic reviews at -4 and -1 weeks and then every 6 months (black arrows). MRI every year (red arrows).

---

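### Pregnancy is tested once, at baseline; none of the four later study infusions requires a negative test, and confirmed pregnancy is not a named reason to stop study drug

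*Protocol*

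**What the plan says.** All references are to the protocol.

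- **Entry (section 3.c).** Pregnancy and lactation are exclusions. So is being "Unwilling or unable to use appropriate contraception for the treatment phase of the study (2 years"; this applies to men and women.
- **Testing (section 3.h).** The visit list contains one pregnancy test. It is part of the bloods at the "Baseline/enrolment Visit (-7 - -4 days", where the item reads "Lymphocyte subsets, bHCG (in women".
- **Dosing (Figure 1 and section 3.h).** The study drug schedule is "Rituximab/placebo administered at Weeks 10 and 30 in each of Years 1 and 2". The visit list gives the condition for dosing: "Intervention visits (At weeks 10 and 30 provided B-cell count >30% of pre-treatment level". The items under that heading are loratadine, methylprednisolone and rituximab or placebo.
- **Risk mitigation (section 3.f).** The same single condition appears: "rituximab administration will be delayed if B-cell counts do not exceed 30% of pre-treatment levels".
- **Stopping rules (section 3.g).** Study drug stops at the participant's own choice, or after a serious adverse event that is suspected to be drug-related or that compromises adherence. In the second case "the intervention will be ceased; however, the participant will remain in the trial and will be followed-up through to the end of the study". Pregnancy is not named.

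**The concern.** The contraception criterion shows that the sponsor wants pregnancy avoided throughout dosing and not only at entry. Yet the protocol checks this once, before any treatment, and then sets a dosing rule with a single condition unrelated to pregnancy. At stake is participant safety. A woman who conceives after baseline and does not know it could receive the trial's own infusion, and the site would have committed no deviation.

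This belongs in the protocol. Conditions for giving study drug and reasons for stopping it are not matters that a statistical analysis plan would settle.

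**Working it through.** The protocol gives no figure to reproduce here, so the check sets the schedule side by side and counts.

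**Number and timing of infusions.** 2 per year x 2 years = 4. In Table 3 the alemtuzumab courses are at weeks 0 and 52, so the infusions fall at weeks 10, 30, 52 + 10 = 62 and 52 + 30 = 82. Table 3 shows the same weeks.

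**Time from the only test.** The test is 4 to 7 days before day 0, so the interval is 7 x week + 4 to 7 x week + 7 days.

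**Last listed contacts before each infusion.** Review weeks (25, 51, 77) and lymphocyte-subset draws (9, 26, 61, 78) are taken from the visit list in section 3.h.

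| Infusion | Week | Days since the bHCG test | Last 6-monthly review | Last lymphocyte-subset draw | Negative test required |
|---|---|---|---|---|---|
| 1 | 10 | 74–77 | none since enrolment | week 9 (1 week before) | no |
| 2 | 30 | 214–217 | week 25 (5 weeks before) | week 26 (4 weeks before) | no |
| 3 | 62 | 438–441 | week 51 (11 weeks before) | week 61 (1 week before) | no |
| 4 | 82 | 578–581 | week 77 (5 weeks before) | week 78 (4 weeks before) | no |

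Pregnancy tests listed after baseline: 0. Infusions conditional on a negative test: 0 of 4. The intervals show only that the baseline result says nothing about pregnancy on the day of an infusion. They do not measure harm.

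**Other contacts that might close the gap.**
- Monthly Bloodwatch tests are described in sections 3.f and 3.h. They cover blood count, renal function, urine red cells and protein or albumin, and 3-monthly TSH; section 3.h adds liver tests and lymphocyte subsets. No pregnancy test is named. One figure inside the section 3.h list is not reproduced in the text read.
- The alemtuzumab admissions, including the Year 2 course, list none.
- The 6-monthly reviews list relapses, adverse events, intercurrent illness, concomitant medication and EDSS. They list neither a pregnancy test nor a contraception check, and they may be held by telehealth.

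Table 3 is a summary of participant time, so the absence of a pregnancy-test row there is not used as evidence.

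**Burden of the fix.** Table 3 allots 4 hours to each infusion visit: 4 x 4 h = 16 h = 960 minutes. Assume 5 to 10 minutes per urine test (the protocol gives no figure): 4 x 5 = 20 to 4 x 10 = 40 minutes per woman. That is 20/960 = 2.1% to 40/960 = 4.2% of infusion-visit time, with no extra visit.

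**The case against.** The case on the other side is that this is an argument from silence, and that the plan already has safeguards.

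- **Contraception.** The criterion covers 2 years (104 weeks), so it spans the last infusion at week 82. This stands, but it is judged as willingness and ability at entry, and no later check is listed.
- **Reviews.** Those at weeks 25 and 77 come 5 weeks before infusions 2 and 4. They could reveal a known pregnancy or a change in hormonal contraception.
- **Link to alemtuzumab.** If a course is moved for clinical reasons, "the timing of rituximab administration will be adjusted accordingly but the timing of all other study related procedures will remain unaltered". A recognised pregnancy that deferred course 2 would therefore also defer infusions 3 and 4.
- **Text not available.** The consent form was not available to read, and it could carry instructions on contraception and on reporting pregnancy. This cannot be excluded.
- **Size.** The protocol describes no fetal risk from rituximab and gives neither a sex split nor a conception rate. Harm is inferred from the sponsor's own exclusions and cannot be quantified.

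These points narrow the gap mainly to unrecognised pregnancy; none of them would detect one. Sites may also test under usual care, but the protocol does not say so, and these infusions are the trial's own intervention.

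Two stronger readings are tempting and are not supported. A reader might infer that the protocol contradicts itself. It does not: an entry criterion and a dosing rule that omits the same subject can both be followed. A reader might also take 0 of 4 to mean that nothing protects participants after baseline. The safeguards above show otherwise.

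**Conclusion.** The point holds as a gap in the dosing rule. In the visible protocol there is one pregnancy test and four later infusions, none of them conditional on a negative result, and pregnancy is not a named reason to stop study drug. An unrecognised pregnancy could be dosed within protocol.

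The conclusion assumes that neither the consent form nor the figure missing from the Bloodwatch list adds a test or a pregnancy rule for the infusions. It does not say that exposures are likely or how many there would be. It does not touch the primary analysis method or the sample size. It is worth correcting because the remedy is small and specific and serves an aim that the sponsor has already stated.

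**What to change.** 1. In section 3.f and under the intervention visits in section 3.h, add a second condition beside the B-cell count. For women who could become pregnant, require a negative pregnancy test before each study infusion. Use either a urine test on the day, before pre-medication, or a serum bHCG within a short stated window before dosing.
2. The serum option may use an existing draw. The lymphocyte-subset draws at weeks 9 and 61 are one week before infusions 1 and 3. Those at weeks 26 and 78 are four weeks before infusions 2 and 4, so a later sample or a urine test on the day would suit these better.
3. Tie the test to the infusion and not to a calendar week, because infusions can be delayed or moved.
4. If the test is positive, withhold the dose and confirm with serum bHCG. A single unconfirmed urine result should not end treatment: stopping at infusion 1 would forfeit all four doses.
5. If pregnancy is confirmed, stop study infusions and continue follow-up. Add confirmed pregnancy to the stopping rules in section 3.g, which already stop study drug and keep follow-up after certain serious adverse events.

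The cost is up to four inexpensive tests per woman, about 2% to 4% of infusion-visit time under the assumption above, and an occasional delayed or withheld dose.
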